## Funder

This research project is part of a MSc. project within the Scientist Training Programme.

This protocol describes this study and provides information about procedures for entering participants. Every care was taken in its drafting, but corrections or amendments may be necessary. These will be circulated to investigators in the study. Problems relating to this study should be referred, in the first instance, to the Chief Investigator. This study will adhere to the principles outlined in the UK Policy Frame "Work for Health and Social Care Research." It will be conducted in compliance with the protocol, the Data Protection Act and other regulatory requirements as appropriate.

## GLOSSARY OF ABBREVIATIONS

PTA	Pure Tone Audiometry
DPOAE	Distortion Product Otoacoustic Emissions
MEMR	Middle Ear Muscle Reflex
EHF	Extended High Frequency
TFI	Tinnitus Functional Index
SiN	Speech in Noise
HL	Hearing Loss
NIHL	Noise Induced Hearing Loss
WHO	World Health Organisation
NESI	Noise Exposure Structure Interview

## STUDY SUMMARY

TITLE	Does Sound Conditioning Protect Against Temporary Hearing Damage?
DESIGN	Between Groups Trial
AIMS	To investigate if previous sound conditioning reduces susceptibility to TTS and tinnitus when comparing to those without prior exposure
OUTCOME MEASURES	EHF PTA, DPOAE, MEMR, TFI, SiN Test
POPULATION	40 Normal Hearing, Healthy 18-35 year olds
DURATION	July 2019 – May 2020

## 1. INTRODUCTION

### 1.1 BACKGROUND

This research project will contribute to the research surrounding the effect on the cochlea after noise exposure; this ever growing field of research has never been more applicable than now with the increase of recreational noise exposure.

Hearing Loss (HL) is becoming more prevalent in today's world, and is the most common sensory deficit. Over 5% of the world's population, over 360 million people, have disabling HL (World Health Organisation [WHO], 2015). This is defined by WHO as a moderate HL where hearing thresholds are greater than 40 dB HL. This figure is expected to be closer to 900 million by 2050. In the U.K. alone, latest figures suggest one in six of the population have some form of HL. By 2035, it is estimated that this will increase to one in five (Action on Hearing Loss [AoHL], 2016).

Noise is the leading cause of preventable hearing loss and second only to presbycusis (age-related hearing loss) for the most common sensorineural hearing deficit. Excessive occupational noise along with recreational noise exposure can cause a devastating disability. In a world where cities never sleep, traffic never stops, phones require devotion and there is constant noise coming from all directions, it is no surprise that noise itself is one of the most common pollutants. Generally, environmental sounds are at safe levels but sounds can become harmful when too loud and worse when they are long-lasting too. As noise damage usually occurs gradually early in life, it is typically not perceived until it worsens with age and becomes more pronounced and noticeable. At this stage it can cause worse debilitating effects i.e. social isolation. In recent research, there is much more focus concerning young people and excessive exposure to recreational noise. On the 3rd of March 2018, World Hearing Day (WHO) focused on 'Hear the future' to highlight preventative measures and management strategies to address the anticipated rise in hearing loss prevalence globally. WHO estimates 1.1 billion young people could be at risk of hearing loss due to unsafe practice listening practices.

Currently, understanding of NIHL is unclear. There is a reliance on clinical Pure-Tone Audiometry (PTA) results typically from 0.25 Hz to 8 kHz to reveal a characteristic dip/notch in the audiogram between 3 kHz and 6 kHz. An expansion of knowledge and understanding of how noise exposure impacts hearing is required, in order to have better preventative measures and treatments in place.

### 1.2 RATIONALE FOR CURRENT STUDY

One of the mechanisms shown to increase the resistance against Noise Induced Hearing Loss (NIHL) is 'sound conditioning'. Animal studies have found that prior exposure to low level noise over a period of a few weeks can 'condition' the ear. This conditioning then reduces the susceptibility to

high level exposure i.e. strengthening the cochlea. However, the underlying mechanisms are not yet clarified. This conditioning may be related to: increased levels of antioxidant enzymes, neurotropic factors, inhibition of apoptosis along with many other speculations. Speculation has also occurred with regards to conditioning acting systemically or locally. Animal studies in regards to NIHL and conditioning suggest with prior exposure there is less risk than those with little exposure before experiencing one high exposure event. There are gaps however in the knowledge on the effects of conditioning in humans. A study where humans are tested prior and post a high-exposure event with varying previous noise exposure history ('conditioning') is not yet available. The relations between temporary threshold shift (TTS), speech in noise, tinnitus, and sex are currently unknown and require further investigation.

There are many implications of this research. For one it will allow us to understand more about the susceptibility to exposure of sounds and the resistance against NIHL. This will mean that we can enable appropriate interventions if necessary. For example, an individual who is more susceptible due to low prior exposure may be advised that they are at risk, and encouraged to use hearing protection. We will be able to learn more about the impacts of noise with hearing and educate others such as understanding the impacts from high-level exposure.

## **2. STUDY OBJECTIVES**

- i) To identify if there is a relationship between previous sound exposure levels and TTS and tinnitus after a single loud noise event.

## **3. STUDY DESIGN**

Type of Study: Basic Science Study, Between Groups Trial

Aim: To investigate if previous sound conditioning reduces susceptibility to TTS and tinnitus when comparing to those without prior exposure.

Purpose: To increase our understanding on the effects of noise exposure.

Duration: Data collection will be completed by February 2020

Participants: 40 normal hearing young (18-35) participants in good general health and fluent in English.

Spilt into groups of two. One group (20, 10f:10m) with previous exposure i.e. nightclubs ++, the other group (20, 10f:10m) with less exposure measured through NESI.

### **3.1 STUDY OUTCOME MEASURES**

The participants will need to attend three sessions which will take approximately 35 minutes, 105 minutes overall. Participants will be required to attend testing before, after a high exposure event they would usually find themselves in, and a week later to test recovery. The results will be evaluated and available on request by 04/04/2020. The outcome measures are the Extended Frequency (EF) PTA, Distortion Product Otoacoustic Emissions (DPOAE), Tinnitus Functional Index (TFI), Middle Ear Muscle Reflex (MEMR) and Speech in Noise (SiN) Test.

### **3.2 METHODS**

Screening - Participants will be asked about the health of their ears and ears will be examined to ensure there are no abnormalities (Otoscopy). A hearing test (PTA) will then be performed; This test will involve participants listening to a series of tones at different pitches and volumes through headphones and participants will press a button whenever they hear a tone. The researcher will also undertake a structured interview to assess noise exposure history (NESI) and the results from the screen will see if you are eligible to participate in this research. With participants consent, if any abnormalities are detected at any point, your GP will be informed with a copy of the results. Participants will subsequently be excluded from the study and information destroyed. Example of NESI question: I'd like you to estimate how noisy it was when you [engaged in the activity] by answering this question: If you and I were 4 feet apart in that situation, which of the following would you need to do to communicate with me? [The interviewer presents the six options from the Speech Communication Table.]

Each session will require 35 minutes (35 x 3 = 105 minutes overall).

SESSION ONE - Prior to noise exposure (continued same day after screening passed if eligible):

Test battery - High frequency audiometry, Distortion Product Otoacoustic Emissions, Middle Ear Muscle Reflex, Speech in Noise test, Tinnitus Functional Index (Around 35 minute testing time with breaks if required)

- Extended Frequency Pure Tone Audiometry (~ 8 minutes)

Similar to Screening, participants will be asked to press the button when they hear a sound through the headphones in a sound proof booth.

- Distortion Product Otoacoustic Emissions (~ 5 minutes)

A small tip will be placed in participants' ear and they will hear a sound. The tip measures a response from hair cells in the cochlea and they will not need to do anything.

- Middle Ear Muscle Reflex (~ 8 minutes)

A small tip will be placed in both ears and again a sound heard however this sound will gradually get louder until an involuntary muscle reflex is noted.

- Speech in Noise Test (~ 5 minutes)  
Participants will be asked to repeat back a list of words as best as they can.
- Tinnitus Functional Index (~ 8 minutes)  
Participants will be given a self-report sheet in which they have to fill out aspects of any tinnitus experienced.

SESSION TWO - Exposure at single loud music event (Important that this is part of participants' normal recreational routine, and specifically require that attendance is not prompted by participation in this study): Participants to use sound level meter provided from the Audiology Department at Charing Cross Hospital to measure sound levels inside the loud event.

Morning after exposure: Repeat test battery from session one - Ideally as soon as event is over.

SESSION THREE: 1 week later (recovery): Repeat test battery.

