## 7. STATISTICS AND DATA ANALYSIS

The quantitative data will be analysed by the researcher at Charing Cross Hospital, Imperial Healthcare NHS Trust. Data and all appropriate documentation will be stored for a minimum of 5 years after the completion of the study, in line with trust protocol.

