### 8.3 CONFIDENTIALITY

The Principal Investigator will preserve the confidentiality of participants taking part in the study. All information which is collected during the research will be kept strictly confidential. Participants will be given a unique ID number as a substitute for personal information and this will be attached to any results from tests. This will be kept in compliance with the Data Protection Act. This anonymised data will be stored and may be published. Any other personal information will be stored on a password-protected database and only accessible to the Principle Investigator. This will be kept separately from documentation of results, ensuring information is not matched and avoid accidental identification. The NESI Structured Interview will be recorded on a digital device and transcribed; any recorded data will then be destroyed from the digital device. All of the data will be kept for 5 years as per study policies.

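### The researcher takes the group-defining noise history before the outcome battery and also analyses the data, with no masking described; separate session sheets and analysis code locked on coded labels are a cheap, partial safeguard

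*Combined protocol and SAP*

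**What the plan says.** **Groups.** Section 3 (Study design) plans 40 participants in two groups of 20, each 10f:10m. The groups differ in past noise exposure, with NESI as the measure. They are not randomised.

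**Order of events.** Section 3.2 lists ear examination and a hearing test at screening, and then: "The researcher will also undertake a structured interview to assess noise exposure history (NESI"). It adds that "the results from the screen will see if you are eligible to participate in this research". Session one, the baseline battery, is "continued same day after screening passed if eligible". The later sessions read "Morning after exposure: Repeat test battery from session one" and "SESSION THREE: 1 week later (recovery): Repeat test battery".

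**Who tests.** Section 3.2 describes the battery without naming a tester or scorer. For speech in noise it says only: "Participants will be asked to repeat back a list of words as best as they can".

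**Who analyses.** Section 7: "The quantitative data will be analysed by the researcher". The rest of that section covers location and data retention. It gives no test, model, significance level or primary outcome.

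**Coding.** Section 8.3 assigns ID numbers and stores personal data apart from results, as confidentiality measures. It also says "The NESI Structured Interview will be recorded on a digital device and transcribed". No section describes masking. A statistician and a trial coordinator appear only in the authorship rule of section 10.

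**The concern.** The hypothesis has a direction: people with more past exposure should show less temporary threshold shift (TTS). A tester who knows the noise history and holds that expectation can, without meaning to, treat borderline responses differently in the two groups. A tester who can also see the earlier thresholds can anchor on them. An analyst who knows the groups, and has no pre-specified analysis, can choose frequencies, ears, cut-offs or exclusions in the light of the group contrast.

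The study is not randomised and its analysis is not fixed, so nothing else in the plan limits these two routes. At stake is whether a group difference in the behavioural measures can be read as an effect of conditioning.

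**Working it through.** **1. What the text establishes.**
- The researcher conducts NESI: stated (section 3.2).
- NESI separates the groups: stated (section 3).
- NESI comes before all three outcome batteries: stated (section 3.2). The screening hearing test is listed before NESI, so the ordering point applies to the outcome battery only.
- The researcher analyses the data: stated (section 7).
- The researcher runs and scores the battery: not stated. It is a reasonable inference for an MSc project.

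**2. Which tester bias survives.** TTS is post-event minus baseline. Let t(g,s) be the tester's average shift in group g at session s. The bias in the group difference in change is

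[t(high,post) − t(high,base)] − [t(low,post) − t(low,base)].

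If each group's shift is the same at both sessions, both brackets are zero. Only a shift that differs by group and by session remains. A tester who expects less TTS in the exposed group would produce that kind, because the expectation concerns the post-event result.

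**3. Which outcomes are open to it.**
- Extended-frequency audiometry (button press) and speech in noise (spoken words): open.
- Middle ear muscle reflex: open if the reflex is judged by eye, which section 3.2 leaves unclear.
- DPOAE: little affected, since the participant does nothing.
- Tinnitus Functional Index: self-report by someone who knows their own noise history. Masking staff does not protect it.

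**4. Illustrative size.** There is no plan figure to reproduce: the 40 comes with no alpha, power, effect size or SD. Inputs: n = 20 per group (section 3); two-sided alpha 0.05 (assumed); no true effect; residual bias b, in SDs of the change score (assumed). For a two-sample t-test, df = 38 and the noncentrality is b × √(20/2) = 3.162b.

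| b (SD) | Noncentrality | False-positive rate |
|---|---|---|
| 0 | 0 | 5.0% |
| 0.1 | 0.316 | 6.1% |
| 0.2 | 0.632 | 9.5% |
| 0.4 | 1.265 | 23.4% |

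In decibels the answer depends on the SD of the change, which is also assumed. A differential bias of 2 dB gives 53.8% at an SD of 3 dB (2/3 = 0.67 SD), 23.4% at 5 dB (0.40 SD) and 14.3% at 7 dB (0.29 SD).

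For scale, 20 per group has 80% power at d = 0.909 under the same test. A bias of 0.1 to 0.4 SD is 0.1/0.909 = 11% to 0.4/0.909 = 44% of that difference.

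**The case against.** The strongest reply has three parts.

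First, the protocol never says that the interviewer also tests. This stands: the tester route is conditional on it. The analyst route is not, because section 7 names the researcher.

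Second, a tester who is biased to the same degree throughout does no harm, because the bias cancels in the change score. This stands too, and limits the concern to bias that differs between sessions. It does not remove it, since the expectation is about the post-event result.

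Third, the bias sizes are assumed. They are, and the rates above show only how sensitive 20 per group would be.

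A reader might also infer that moving NESI behind the baseline battery, or leaving its recording unscored until after session three, would solve the problem with no new staff. The documents do not support this:
- Masking baseline alone sets t(high,base) and t(low,base) to zero in step 2 and leaves the post-event terms. A bias that would have cancelled then no longer does.
- Leaving the recording unscored does not mask an interviewer who has heard the answers.
- Section 3.2 makes NESI part of the screen that decides eligibility, and section 3 needs it to fill 20:20 with 10f:10m. Sections 4.3 and 4.4 state no NESI threshold, so the eligibility conflict may be small, but the group quotas could no longer be steered.

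**Conclusion.** The point holds as a modest, low-cost improvement. The researcher knows the group-defining history before the outcome battery and analyses the data, no masking is described and no analysis is fixed in advance. If the same person tests, audiometry and speech in noise are exposed, and the reflex measure possibly so.

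The magnitude is unknown. The range of about 6% to 23% rests on an assumed two-sided 5% test, no true effect, and an assumed bias of 0.1 to 0.4 SD that differs by group and session.

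Two stronger readings go too far. A reader might infer that tester expectation is likely to produce the group difference; the documents neither name the tester nor give any basis for the size of such a bias. A reader might also infer that the bias is as large as the effect sought; no effect sought is stated, and the illustrative bias is well below what 20 per group could detect with 80% power.

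**What to change.** Keep NESI at screening, so that eligibility and the 20:20, 10f:10m groups can still be set. Do not move it behind the baseline battery only, and do not defer its scoring until after session three. Then:

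1. State in section 3.2 who runs and scores the battery, and what that person knows.
2. Record each session on a fresh sheet, with earlier thresholds and NESI results out of the tester's view.
3. Write and lock the analysis code on shuffled or coded group labels, and attach the true labels only afterwards. This works even when one person does everything, because the choices are made before the real contrast is seen.
4. Interpret the audiometric result alongside DPOAE, which is already collected and needs no participant response.

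The cost is slight extra record-keeping, with no new staff and no change to recruitment or visits. Two limits remain. If the interviewer also tests, tester masking is partial, because that person has heard the answers. The Tinnitus Functional Index is not protected by any of these steps.

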### 4.3 INCLUSION CRITERIA

- 18-35 years old (as age can affect cochlea hair cell function)
- Healthy participants with no significant medical conditions
- 0.25 Hz to 8 kHz PTA in both ears have thresholds  $\leq$  20 dB HL indicating normal hearing
- Otoscopy to ensure no otological abnormalities
- No exposure to abnormally loud sounds in the past 24 hours
- Full capacity to consent

- Able to speak fluent English so information sheets, consent forms and instructions are fully understood
- Previous intention to attend a loud noise event during the course of the study, without the use of hearing protection

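### Time since the last loud noise is neither controlled nor recorded at sessions two and three, so a new loud night before session three would read as incomplete recovery

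*Combined protocol and SAP*

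**What the plan says.** **Session two.** Section 3.2 gives the timing as "Morning after exposure: Repeat test battery from session one - Ideally as soon as event is over". Section 3.1 says only that testing takes place "after a high exposure event they would usually find themselves in, and a week later to test recovery". Neither gives an earliest or latest hour. The one measurement requested at the event is its sound level.

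**Session three.** Section 3.2 reads "SESSION THREE: 1 week later (recovery): Repeat test battery". Section 6 confirms a one-week test of recovery and adds no condition on noise beforehand.

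**Quiet condition.** Section 4.3 lists "No exposure to abnormally loud sounds in the past 24 hours" as an inclusion criterion. It covers session one because that session is "Prior to noise exposure (continued same day after screening passed if eligible".

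**Noise history.** Under Screening in section 3.2: "The researcher will also undertake a structured interview to assess noise exposure history (NESI"). The battery repeated at sessions two and three is "Test battery - High frequency audiometry, Distortion Product Otoacoustic Emissions, Middle Ear Muscle Reflex, Speech in Noise test, Tinnitus Functional Index", which contains no question about recent noise.

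**Groups.** Section 3 forms them by noise habits: "One group (20, 10f:10m) with previous exposure i.e. nightclubs", against a group with less exposure on the NESI.

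**Analysis.** Section 7 names no adjustment for delay or for other exposure.

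**The concern.** The outcome is a temporary shift, so any reading depends on how long ago the last loud noise was. The protocol accepts this at entry by asking for 24 quiet hours, but does not carry the idea forward to the later sessions.

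Session three is the only recovery test. A participant who has been to another loud event the night before may show a shift that has nothing to do with the index event. Unless someone asks, this cannot be told apart from slow recovery. Because the groups are formed by noise habits, such nights could plausibly be commoner in the exposed group. A loud night between session one and the index event raises a similar problem for session two.

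The delay from event to session-two test matters less. If it varies in the same way in both groups, it adds scatter. It biases the comparison only if it differs by group, and without recorded times nobody could check. Times and exposures not written down at the visit may not be reliably recoverable later.

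**Working it through.** **Step 1: the text.** The five places where a rule or question could sit, side by side:

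| Item | Entry / session one | Session two | Session three |
|---|---|---|---|
| Window in hours | not needed | none | one week, no tolerance |
| 24-hour quiet condition | yes (4.3) | none before the index event | none |
| Noise question | NESI (3.2, Screening) | none | none |
| Event-end and test times | not applicable | not requested | not requested |
| Adjustment in analysis | none (7) | none (7) | none (7) |

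**Step 2: inputs for size.** The plan states no figure on this point, so there is none to reproduce. It gives no initial shift, recovery rate or SD. Everything below is assumed and concerns hearing thresholds only; no size is offered for the other four outcomes.

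- Initial shift T0 = 10 or 15 dB at t0 = 2 minutes.
- Log-time decay to zero at tend = 24, 72 or 168 h: TTS(t) = T0 × [1 − ln(t/t0) / ln(tend/t0)].

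**Step 3: residual at session three after a night out 10 h earlier.** ln(10 h / 2 min) = ln 300 = 5.704. The denominators are ln 720 = 6.579, ln 2160 = 7.678 and ln 5040 = 8.525. The fractions left are 1 − 5.704/6.579 = 0.133, then 0.257 and 0.331.

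| | 24 h | 72 h | 168 h |
|---|---|---|---|
| Residual, T0 = 10 dB | 1.3 | 2.6 | 3.3 |
| Residual, T0 = 15 dB | 2.0 | 3.9 | 5.0 |
| Group gap, 30% v 10% out (0.2 × residual) | 0.3-0.4 | 0.5-0.8 | 0.7-1.0 |
| Group gap, 50% v none out (0.5 × residual) | 0.7-1.0 | 1.3-1.9 | 1.7-2.5 |
| Residual if the night out was 24 h earlier | 0 | 1.4-2.1 | 2.3-3.4 |

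The gap is zero if both groups go out equally often.

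**Step 4: a different curve.** With exponential recovery, TTS(t) = T0 × 0.5^(t/h), the fraction left at 10 h is 0.177 for a half-life h of 4 h and 0.749 for 24 h. That is 1.8-2.7 dB and 7.5-11.2 dB. The gap at 30% v 10% is then about 0.4-2.2 dB, and at 50% v none about 0.9-5.6 dB. At 24 h, a 24 h half-life still leaves 0.5 × 10-15 = 5.0-7.5 dB. The log-time figures are therefore not upper limits.

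**Step 5: session-two delay as scatter.** Take an SD of 5 dB (assumed) and add the SD that the decay curve produces when delay is uniform over a range.

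- Delay 6-12 h: log-time decay adds an SD of 0.23-0.45 dB, so √(25 + 0.45²) = 5.02. The largest of the exponential cases tried (half-lives 4, 8, 16 and 24 h) adds 1.04 dB, so √(25 + 1.04²) = 5.11.
- Delay 1-12 h: log-time decay adds 0.73-1.42 dB, so √(25 + 1.42²) = 5.20. The largest exponential case adds 3.01 dB, so √(25 + 3.01²) = 5.84.

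If instead one whole group were tested at 6 h and the other at 10 h, the log-time curve gives a false difference of 0.6-1.2 dB.

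**The case against.** **A reader might infer that session two has two contradictory targets.** The text does not require that reading. It can be taken as one target, the morning after, with a preference for early in that slot. The absence of a window and of any recorded delay stands either way. The 1-12 h spread in the working depends on the wider reading; on the narrower one the added scatter is small.

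**A reader might infer that the comparison is biased.** The documents do not show that loud nights before session three, or delays to session two, differ by group. Everyone enrolled must already intend to attend a loud event (section 4.3), so none in the less exposed group is an extreme case. That is why 30% v 10% is shown beside it.

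**A reader might infer that this could manufacture a protective effect.** If extra nights out are commoner in the exposed group, the error runs the other way: that group looks slower to recover, so protection could be masked, not created.

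**Reach.** The objective in section 2 is shift and tinnitus after a single event. Recovery is measured but not named there, so the session-three problem bears on the recovery result rather than the stated objective. This stands. A loud night between session one and the index event could touch the objective, but the documents give nothing from which to size it.

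**Other defences.** The sound level meter might log times, but the protocol does not ask for them. Title and other pages were removed before review, so the absence is from the text available.

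**Conclusion.** The point holds in a limited form. Session two has no window in hours, the delay is not recorded, and after entry nothing restricts or asks about other loud events. Followed as written, the plan could not separate a fresh exposure from slow recovery at session three.

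The consequence is conditional. It becomes a group bias only if other loud events differ by group. Under log-time decay, the false gap in thresholds is then about 0.3-1.0 dB at 30% v 10%, and 0.7-2.5 dB in the extreme case. Other curves give more. Session-two delay mainly adds noise unless it differs by group. All sizes rest on assumed shifts, recovery curves and proportions, so they show direction and rough scale only. This is a cheap improvement, not a flaw that invalidates the design.

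**What to change.** - State one session-two window in hours from the end of the event, the same for both groups.
- At sessions two and three, record event-end time, test time, last loud exposure and any other loud events since the previous session.
- Apply the existing 24-hour condition before session three. Hold any rescheduling to a stated maximum window common to both groups; otherwise test and flag. Without that cap, the group that goes out more could be tested later after the index event, which would introduce a new imbalance.
- Report time since last loud exposure by group.
- Add a sensitivity analysis that adjusts for session-two delay and excludes or flags participants with other loud events.

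The 24-hour condition clears the residual only if recovery is complete by then, which step 3 of the working shows is not assured. The recorded times therefore do most of the work.

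The cost is protocol wording, a few questions per visit, some rescheduling of session three, and a slight loss of precision in the sensitivity analysis with 20 per group.
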